8.18.3 Assessment of Severity

The severity (or intensity) of an AE will be classified using the following criteria:

- Mild: These events are usually transient, require minimal or no treatment, and do not interfere with the subject's daily activities.
- Moderate: These events result in a low level of inconvenience or concern with the therapeutic measures. Moderate events may cause some interference with normal functioning but pose no significant or permanent risk of harm.
- Severe: These events interrupt a subject's usual daily activity and may require systemic drug therapy or other treatment. Severe events are usually incapacitating.

Changes in the severity of an AE should be documented as a new event to allow an assessment of the duration of the event at each level of intensity to be performed.

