5 INVESTIGATIONAL PLAN

5.1 Overall Study Description

This is an open-label Phase 1b study evaluating oral omadacycline in the treatment of adults with CABP.

This study is intended to evaluate the PK of an oral dosing regimen in adults with CABP. Subjects will initiate treatment with an oral loading dose of 300 mg BID on Day 1 followed by 300 mg QD on subsequent days.

Following a screening period of up to 24 hours, eligible subjects will be assigned to receive 7 to 10 days of po treatment. Subjects with baseline bacteremia (ie, confirmed from local blood culture drawn at screening) can receive up to 14 days of treatment after consultation with the medical monitor.

Subjects may receive oral treatment in either inpatient or outpatient settings, provided that all assessments can be completed at the timepoints required by protocol.

Test Article	Study Day	Study Day	Study Days 3-10
Omadagualina	1	 	
Omadacycline	300 mg po BID	300 mg po QD	300 mg po QD
po = per oral, a dosing day is a 24-h	our day not a calendar d	lay	
a The total duration of treatmen	t is 7 to 10 days. Treatn	nent duration can be ext	tended to up to 14 days for
subjects with bacteremia that, in	n the opinion of the inve	estigator, requires more	than 10 days of treatment.

Eligible subjects will be assigned to the following treatment groups.

Refer to the Schedule of Events (Appendix 1) for the summary of subject visits and assessments through end of treatment (EOT).

Subjects will return to the study site for a Post Therapy Evaluation (PTE) 5 to 10 days after the last dose of test article. A Final Follow-up visit (FFU) will be conducted within 30 to 37 days following the first dose of test article. The FFU assessment may be conducted via telephone contact or by another interactive technology for subjects who had an outcome of Clinical Success in the opinion of the investigator at EOT and PTE and had no AEs or clinically significant laboratory or electrocardiogram (ECG) abnormalities noted at or after the PTE visit. Otherwise, this assessment is to be performed with an in-person study visit.

The planned length of subject participation in the study is up to 37 days.

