8 STUDY PROCEDURES

Written, signed, and dated informed consent will be obtained before any study-related procedures have been performed. Upon signing the informed consent, the subject will then be assigned a study subject number. Adverse events (AEs) must be recorded from the time the ICF is signed. Subjects who have been pre-screened on the telephone but who do not sign an ICF will not be assigned a subject number. The investigator will maintain a subject master list to document every subject who has signed an ICF. A copy of this list should be retained in the investigator's study files.

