12.6 Secondary Endpoint(s)

12.6.1 Safety Endpoint(s)

All safety analyses will utilize the Safety population. Summary tables will be provided for all treatment-emergent adverse events (TEAEs). A TEAE is defined as an AE with a start date and time on or after the first dose of test article. Adverse events will be coded using the Medical Dictionary for Regulatory Activities (MedDRA) and will be summarized by presenting the number and percentage of subjects having each TEAE by system organ class (SOC) and preferred term (PT), by SOC, PT and severity, and by SOC, PT and relationship to test article. Additional tabulations will provide summarise by SOC and PT of subjects experiencing SAEs and TEAEs leading to discontinuation of test article. Treatment-emergent adverse events leading to dose interruption of test article, and TEAEs of special interest.

The following variables will be analyzed descriptively in the Safety population:

- Vital signs (systolic and diastolic BP, pulse/heart rate, body temperature, pulse oximetry, RR), including change from Baseline by time point measured
- Clinically notable vital signs (meeting predefined criteria as specified in the SAP) by time point measured
- Laboratory parameters, including change from Baseline by visit and overall worst post-baseline
- Clinically notable laboratory parameters (meeting predefined criteria as specified in the SAP) by visit and overall worst post-baseline

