8.1 Adverse Events

Verbatim descriptions of AEs will be coded using Version 17.1 or higher of MedDRA. Summary tables will be provided for all treatment-emergent adverse events (TEAEs), but all AEs will be provided in a listing. A treatment-emergent AE is defined as any AE that newly appeared, increased in frequency, or worsened in severity on or after the initiation of active test article. An AE is considered treatment emergent if the AE start date and time is on or after the start date and time of the first dose of active test article. If time of the AE is missing and it occurred on the same date as the first dose of active test article, the AE will be defined as treatment emergent. If the start date of the AE is partial or missing and it cannot be determined if the AE occurred prior to or after the first dose of test article, the AE should be defined as treatment emergent.

An overall summary of AEs will include the number of subjects who experienced at least one AE of the following categories: any AE, any TEAE, any drug-related TEAE, any severe TEAE, any serious TEAE, any drug-related SAE, any serious TEAE leading to death, any TEAE leading to premature discontinuation of test article, any TEAE leading to premature discontinuation from the study, any TEAE leading to dose interruption of test article, and any serious TEAE leading to premature discontinuation of test article.

The number and percentage of subjects reporting a TEAE will be tabulated by system organ class and preferred term; by system organ class, preferred term, and severity (mild, moderate, and severe); and by system organ class, preferred term, and relationship (unrelated or related to test article). The incidence of TEAEs will be summarized by preferred term, sorted by decreasing frequency, for all TEAEs, related TEAEs, serious TEAEs, and TEAEs leading to study drug discontinuation. The incidence of serious TEAEs, TEAEs leading to premature discontinuation of test article, and TEAEs leading to a dose interruption of test article will be summarized by system organ class and preferred term. For all analyses of TEAEs, if the same AE (based on preferred term) is reported for the same subject more than once, the AE is counted only once for that preferred term and at the highest severity and strongest relationship to test article.

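### SAP 8.1 gives two TEAE rules that disagree; under the start-date rule, a pre-dose AE that only improves after Dose 1 is counted as treatment-emergent.

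*Protocol*

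**What the plan says.** Four statements combine.

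- **Recording of severity changes (Protocol 8.18.3).** "Changes in the severity of an AE should be documented as a new event". The stated purpose is to measure how long an event lasts at each intensity. That purpose needs each new record to start on the date of the change, and it covers falls in severity as well as rises.
- **TEAE definition in the protocol (12.6.1).** "A TEAE is defined as an AE with a start date and time on or after the first dose of test article". Start date and time are the only test.
- **TEAE definition in the SAP (8.1).** The opening sentence restricts TEAEs to "any AE that newly appeared, increased in frequency, or worsened in severity on or after the initiation of active test article". The sentence that follows is the one a programmer can apply directly: "An AE is considered treatment emergent if the AE start date and time is on or after the start date and time". Its reference point is Dose 1, and it makes no comparison with severity before dosing.
- **Start of AE collection (Protocol section 8).** "Adverse events (AEs) must be recorded from the time the ICF is signed". Screening may last up to 24 hours (Protocol 5.1), and the first dose is planned for the morning after enrollment (Protocol 7.5.1), so AE records can exist before dosing.

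SAP 8.1 also counts a subject once per preferred term, using the worst severity and the closest relationship among that subject's TEAEs. SAP section 12, which lists departures from the protocol, does not mention the TEAE definition.

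**The concern.** The recording rule breaks one clinical episode into several records, and the start-date rule classifies each record separately. If an AE was present before Dose 1 and becomes milder afterwards, the milder record starts in the treatment period and passes the start-date test. Recovery from a pre-treatment event is then tabulated as an event arising on treatment. The opening sentence of SAP 8.1 would not allow this, since an improvement is not new, more frequent or worse.

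Safety is the only secondary objective, and the TEAE tables (overall, by system organ class and preferred term, by severity, by relationship) are a central part of its reporting. There is one arm, so no concurrent rate shows how much of the incidence comes from record splitting. Two programmers following different sentences of the same SAP section could produce different tables.

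**Working it through.** The plan states no figure for this point, so there is none to reproduce. The check applies the written rules to illustrative AE histories.

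**Rules applied**

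- Record creation: every severity change opens a new record dated at the change (Protocol 8.18.3).
- Rule A, start date: a record is a TEAE if it starts at or after Dose 1 (Protocol 12.6.1; SAP 8.1, second TEAE sentence).
- Rule B, new or worse: a record is a TEAE only if it starts at or after Dose 1 and its severity exceeds the highest pre-dose severity of the same event (SAP 8.1, opening definition made operational).
- Counting: once per preferred term per subject, at the highest severity among TEAE records (SAP 8.1).

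**Results**

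| AE history | Rule A | Rule B |
|---|---|---|
| Severe before Dose 1, moderate after | 1 TEAE, moderate | 0 |
| Severe before Dose 1, then moderate, then mild after | 1 TEAE, moderate | 0 |
| Moderate before Dose 1, unchanged after | 0 | 0 |
| Mild before Dose 1, severe after | 1 TEAE, severe | 1 TEAE, severe |
| New mild AE after Dose 1 | 1 TEAE, mild | 1 TEAE, mild |

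The rules part only where a pre-dose AE improves. Rule A also orders the cases perversely: a moderate AE that stays moderate is not a TEAE, while a severe AE that eases to moderate is.

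**Does the once-per-term rule repair this?** No. It operates among TEAEs. The pre-dose record is not a TEAE, so the improved record is the one counted. The rule only stops the second and third steps of one episode from adding further counts.

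**Size per affected subject.** The protocol plans up to 30 enrolled subjects so that at least 20 are evaluable for bioavailability (12.2). With a denominator of n, one false count adds 1/n to the incidence of that preferred term:

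- n = 30: 1/30 = 3.3 percentage points
- n = 20: 1/20 = 5.0 percentage points

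Overall TEAE incidence moves by the same amount only if the subject has no other TEAE. The documents give no figure for how many subjects would have such an AE, so the total effect cannot be calculated.

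**The case against.** The strongest defence is that the opening sentence of SAP 8.1 is the definition and the start-date sentence is only a timing test within it. On that reading there are no false TEAEs. Protocol 12.1 lets the SAP add to and change the planned analyses, so Protocol 12.6.1 need not control. This is a fair reading, and it limits the point: a reader might infer that the plan certainly counts improving AEs as treatment-emergent, but the documents show only that one of two stated rules does. The defence does not remove the conflict, because nothing says which sentence governs and the start-date sentence is complete as written.

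The second argument is that few subjects are exposed, and it largely stands. A reader might infer that acutely ill patients will bring many pre-dose AEs and so inflate TEAE incidence materially. The documents do not support that. Conditions ongoing at consent are recorded as medical history (Protocol 8.3). Worsening of the qualifying pneumonia is recorded as clinical failure unless it is serious (8.18.5). Laboratory abnormalities are AEs only if clinically significant and unexpected for that subject (8.18.4). The AE must also begin in the short interval between consent and Dose 1, and a mild AE has no lower grade to step down to. The group need not be empty, however, since Protocol 8.3 makes any change in health status after consent an AE.

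Third, the consequences are bounded. The error is at most one count per preferred term per subject. An event that began before any dose should normally be judged unrelated (8.18.2), so related-TEAE counts should be little affected. All AEs are listed with dates, severity and relationship (SAP 8.1), so a reader can find the earlier record. These points stand, but a listing does not correct a summary table.

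**Conclusion.** The point holds as an internal inconsistency in SAP 8.1 that Protocol 8.18.3 turns into a counting problem. Applied as written, the start-date rule classifies a pre-dose AE that merely improves after Dose 1 as treatment-emergent; the opening definition in the same section does not.

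The conclusion assumes that sites follow 8.18.3 for decreases as well as increases, and that the new record carries the date of the change. The number of affected subjects is unknown, probably small and possibly zero. The primary PK analysis is not touched. The case for acting is that a stated rule can give a wrong count and the correction is cheap, not that a large bias has been shown.

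**What to change.** Add one sentence to SAP 8.1, directly after the start-date rule:

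*A record that documents a change in severity of an AE that began before the first dose is treatment-emergent only if its severity exceeds the highest severity recorded for that AE before the first dose.*

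Record this in SAP section 12 as a change from Protocol 12.6.1. Protocol 12.1 allows such a change to be made in the SAP, so a protocol amendment is not needed.

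No new eCRF field is needed either. The records of one episode can be matched by subject, preferred term and contiguous dates, all of which are already captured for the SAP 8.1 listings. New AEs and true worsening are still counted, as the last two rows of the table show. The cost is slightly more AE programming to match the records.

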8.18.4 Laboratory Findings

Protocol-defined safety laboratory test results will be analyzed as part of specific laboratory safety analyses. Additional laboratory test results at other time points may be available to the investigator as part of standard clinical practice. Throughout the study, laboratory-related abnormalities should be recorded as AEs only if considered clinically significant, outside the range of expected values given the subject's Baseline assessments and clinical course, and not known to be part of another AE diagnosis.

8.18.5 Worsening or Progression of Disease Under Study

Worsening or progression of the qualifying CABP should be recorded as a clinical failure (as part of the efficacy assessment), rather than an AE, unless the worsening/progression also meets the criteria for a serious AE (in which case the event also should be reported as an SAE). In contrast, any new or secondary infections that the investigator considers to be distinct from the qualifying CABP should be reported as AEs in all cases, whether non-serious or serious.

8.18.6 Pregnancies

To ensure subject safety, each pregnancy in a subject on test article must be reported to the sponsor within 1 business day of learning of its occurrence. Test article should be discontinued immediately, and the pregnancy should be followed up to determine outcome, including spontaneous or voluntary termination, details of the birth, and the presence or absence of any birth defects, congenital abnormalities, or maternal and/or newborn complications.

Pregnancy should be recorded on a Clinical Trial Pregnancy Form and reported by the investigator to the sponsor. Pregnancy follow-up should be recorded on the same form and should include an assessment of the possible relationship to the test article of any pregnancy outcome. Any SAE experienced during pregnancy must be reported on the SAE Report Form.

8.19 Concomitant Medication Assessments

The investigator should instruct the subject to notify the study site about any new medications they take after the start of the test article.

All prescription medications, over-the-counter drugs, and recreational drugs taken within the timeframe defined in the entry criteria prior to the start of the study and during the study, must be recorded on the Concomitant Medications/Non-Drug Therapies page of the eCRF. Medication entries should be specific to trade name, the single dose and unit, the frequency and route of administration, the start and discontinuation dates, and the reason for therapy.

8.20 Subject Discontinuation or Withdrawal

Reasons why a subject may discontinue or be withdrawn from the study include, but are not limited to, AE, lost to follow up, withdrawal by subject, physician decision, death, and other (specify reason eg, subject non-compliance or study termination by the sponsor). Subjects may voluntarily withdraw from the study for any reason at any time. Subjects are considered withdrawn from the study if they state an intention to withdraw, or fail to return for visits, or become lost to follow up for any other reason. If premature withdrawal from the study occurs for any reason, the investigator should determine the primary reason for a subject's premature withdrawal from the study and record this information on the eCRF.

Subjects who discontinue study treatment should not be considered withdrawn from the study (unless the subject withdraws informed consent). The date and primary reason for discontinuation of study treatment should be recorded. Subjects who discontinue study treatment prematurely should complete the EOT visit, PTE visit and Final Follow-up Assessment, if possible (see Schedule of Events - Appendix 1). The site should also collect subject safety information through the Final Follow-up assessment.

Site personnel should also contact the IxRS, if used to register the subject's discontinuation from test article.

For subjects who are lost to follow up, the investigator should show "due diligence" by documenting in the source documents steps taken to contact the subject, eg, dates of telephone calls, registered letters, etc.

8.20.1 Replacements

Any subject who is withdrawn or discontinued from the study may be replaced at the discretion of the sponsor to meet the target of at least 20 subjects with complete PK sampling.

9 STUDY ACTIVITIES

The full assessment schedule is presented in the Schedule of Events (see Appendix 1). Subjects should be seen for all visits on the designated day.

9.1 Screening Phase

The Screening visit should be completed within a 24-hour period prior to randomization. The Screening procedures will be used to establish subject eligibility and Baseline characteristics for each subject. Following the signing of an ICF, the site staff will collect/perform the assessments detailed in Appendix 1.

9.2 Treatment Phase

The open label treatment period is 7 to 10 days in duration. Additionally, subjects with bacteremia confirmed from local blood culture drawn at screening can receive up to 14 days of treatment. Subjects who meet all of the inclusion criteria and none of the exclusion criteria may be assigned.

9.3 EOT Visit Procedures

The EOT evaluation should be conducted on the day of or within the 2 days following the last dose of test article. If the subject voluntarily withdraws or is discontinued from her dosing regimen, the visit procedures should be performed on that day.

9.4 Follow-up Phase

9.4.1 **Post-Treatment Evaluation Visit Procedures**

The PTE visit should be conducted 5 to 10 days after the last dose. This evaluation should also be conducted for any prematurely withdrawn subject.

9.4.2 Final Follow-up

The FFU assessment should be conducted within 30-37 days following the subject's first dose of test article. This evaluation should also be conducted for any prematurely withdrawn subject with the exception of subjects who withdraw consent. The Final Follow-up assessment may be conducted via telephone contact or by another interactive technology for subjects who are a Clinical Success and had no AEs or clinically significant laboratory, or ECG abnormalities noted at or after the PTE visit. Otherwise, the visit must be conducted in person.

10 STUDY SUSPENSION, TERMINATION, AND COMPLETION

10.1 Study Completion and Post-Study Test Article

A subject will have successfully completed the study after the planned test article regimen has been administered, and all assessments and visits have been performed up through the FFU assessment. The study will be completed when the last subject has either discontinued or completed the FFU assessment.

No long-term follow-up of subjects is planned, with the exception of pregnancies, as described in Section 8.18.6, and SAEs described in Section 8.18.1.

Sites will be notified by either the Sponsor or IxRS, if used to stop enrollment when the desired number of treated subjects have been enrolled. Subjects already consented, but not yet assigned will be allowed to continue Screening procedures.

Upon study completion, the investigator will provide the sponsor, IRB/IEC/REB, and regulatory agency with final reports and summaries as required by regulations. The investigator must submit a written report to the sponsor and the IRB/IEC/REB within 3 months after the completion or termination of the study.

10.2 Study Suspension or Termination

The sponsor may suspend or terminate the study at any time for any reason. Should this be necessary, subjects should be seen as soon as possible and treated as described in Sections 8.20 and 9.3 for prematurely withdrawn subjects. The investigator may be informed of additional procedures to be followed in order to ensure that adequate consideration is given to the protection of the subject's interests. The investigator will be responsible for informing IRBs and/or Ethics Committees (ECs) of the early termination of the study.

If the investigator suspends or prematurely terminates their participation in the study, the investigator will promptly inform the sponsor and the IRB/IEC/REB and provide them with a detailed written explanation. Subjects should be seen as soon as possible and treated as described in Sections 8.20 and 9.3 for prematurely withdrawn subjects. The investigator will also return all test articles, containers, and other study materials to the sponsor.

11 QUALITY CONTROL AND ASSURANCE

The sponsor performs quality control and assurance checks on all clinical studies that it sponsors. Before enrolling any subjects in this study, sponsor personnel and the investigator review the protocol, the Investigator's Brochure, the case report forms (CRFs) and instructions for their completion, the procedure for obtaining informed consent, and the procedure for reporting AEs and SAEs. A qualified representative of the sponsor monitors the conduct of the study by visiting the site and by contacting the site by telephone and e-mail. During these site visits, information recorded in the CRFs is verified against source documents.

